#### 4.2.10.3 Vital Signs

All vital signs variables will be summarised by absolute value at each visit by treatment group, together with the corresponding changes from baseline. This will also include weight, BMI, and height. These summaries will be produced for the on-study period, as defined in Section 3.1.3. The summary statistics presented will be the minimum, 1st quartile, median, 3rd quartile, maximum, mean and SD.

AZ-defined reference ranges (see Section 3.6.5) will be used for the identification of individual abnormalities. A shift table will be produced for each vital signs variable to display low, normal, high and missing values. The shift tables will present baseline and maximum/minimum/last observation values for each variable.

Shift plots showing each individual participant's vital signs value at baseline and at maximum/minimum/last value post-baseline will be produced for each continuous vital signs variable.

Participants who have changes from baseline outside the pre-defined AZ clinically important change criteria defined in Section 3.6.5 will be summarised.

#### **4.2.10.4    Electrocardiogram**

ECG variables will be summarised by absolute value at each visit by treatment group, together with the corresponding changes from baseline. These summaries will be produced for the on-study period, as defined in Section 3.1.3. The summary statistics presented will be the minimum, 1st quartile, median, 3rd quartile, maximum, mean and SD.

A shift table will be produced to display the investigator assessment of normal, abnormal – not clinically significant, abnormal – clinically significant and not done between baseline and end of study. For this purpose, borderline (also recorded on the eCRF) will be grouped with normal.

A frequency table showing participants with Frederician corrected QT (QTc) values and increases from baseline at any time during the on-study period using standard pre-specified thresholds will be produced.

#### **4.2.10.5    Physical Examination**

Clinical signs related to previous serious illnesses as new or worsening abnormalities will be recorded and summarised as AEs. No separate summaries of physical examination findings will be produced.

### **4.2.11    Pharmacokinetics and Immunogenicity**

#### **4.2.11.1    Analysis of Pharmacokinetics**

All analyses of PK variables will be based on the PK analysis set as defined in Section 2.1.3.

Serum tezepelumab concentrations will be summarised over time for the on-study period using descriptive statistics (for the tezepelumab group only).

Serum samples for PK are scheduled to be collected at Weeks 0, 4, 12 24, 36, 52, 64 and at the premature IP discontinuation visit, where appropriate. Data will be assigned to weeks based on the windows defined in Section 3.1.4.

The following criteria will also apply for data to be included in the summary table:

- Only pre-dose samples at Week 0.

- Only pre-dose samples at Weeks 4, 12, 24, and 36 and samples at Week 52 that were also between  $\geq 21$  and  $\leq 35$  days post the previous dose.
- All samples for Week 64 that were taken within the visit window defined in [Section 3.1.4](#).

For descriptive statistics of tezepelumab concentrations:

- If, at a given time point, 50% or less of the concentrations are non-quantifiable (NQ), the geometric mean, coefficient of variation (CV), arithmetic mean and SD will be calculated by substituting the lower limit of quantification (LLOQ) divided by 2 for values which are NQ.
- If more than 50%, but not all, of the concentrations are NQ, the geometric mean, CV, arithmetic mean and SD will be reported as not calculable
- If all the concentrations are NQ, the geometric mean and arithmetic mean will be reported as NQ and the CV and SD as not calculable
- The median, minimum and maximum will also be reported

The LLOQ of tezepelumab in serum will be 0.010  $\mu\text{g}/\text{mL}$ .

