7 DISCONTINUATION OF STUDY INTERVENTION AND PARTICIPANT DISCONTINUATION/WITHDRAWAL

7.1 Discontinuation of Study Intervention

It may be necessary for a participant to permanently discontinue from study intervention. If study intervention is permanently discontinued, the participant will remain in the study to be evaluated for safety as per follow-up. See the SoA ([Table 1](#)) for data to be collected at the time of discontinuation or study intervention and follow-up and for any further evaluations that need to be completed.

Note that discontinuation from study intervention is NOT the same thing as a withdrawal from the study.

See the SoA ([Table 1](#)) for data to be collected at the time of intervention discontinuation and follow-up and for any further evaluation that need to be completed. Participant may be discontinued from IP in the following situations:

- Participant decision. The participant is at any time free to discontinue treatment, without prejudice to further treatment.
- An AE that in the opinion of the Investigator, contraindicates further dosing.
- Severe non-compliance with the CSP.
- Risk to participant as judged by the Investigator or AstraZeneca.
- Pregnancy and breastfeeding.
- IP unblinding (PI).

- Lost to follow-up.
- If participant had undergone NP surgery during the treatment period.
- Development of any study specific criteria for discontinuation:
 - Anaphylactic reaction to IP requiring administration of epinephrine;
 - Development of helminth parasitic infestations requiring hospitalisation;
 - A respiratory-related event requiring intubation;
 - Any malignancy, except participants who develop basal cell carcinoma or localised squamous cell carcinoma of the skin, provided that the malignancy has been excised and determined to have clean margins.
- Development of one or more of the following:
 - Confirmed ALT or AST increase of $\geq 8 \times$ ULN
 - Confirmed ALT or AST increase of $\geq 5 \times$ ULN for more than 2 weeks
 - Confirmed ALT or AST increase of $\geq 3 \times$ ULN and total bilirubin of $\geq 2 \times$ ULN
 - ALT or AST of $\geq 3 \times$ ULN with the appearance of fatigue, nausea, vomiting, right upper quadrant pain or tenderness, fever, rash, and/or eosinophilia ($\geq 5\%$)

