8.3.12.2 Paternal Exposure

Pregnancy of the participant's partners is not considered to be an adverse event. However, the outcome of all pregnancies (spontaneous miscarriage, elective termination, ectopic pregnancy, normal birth or congenital abnormality), occurring from the date of the first dose until 16 weeks (5 half-lives) after the last administration of IP should, if possible, be followed up and documented in the Pregnancy Report Form. Consent from the partner must be obtained before the Pregnancy Report Form is completed.

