## 1.2 Study Design

This is a Phase 3, multicenter, randomised, double-blind, placebo-controlled, parallel-group, study to evaluate the efficacy and safety of repeat dosing of tezepelumab 210 mg SC versus placebo in participants with severe chronic rhinosinusitis with nasal polyposis (CRSwNP).

Approximately 400 participants will be randomised globally in a 1:1 ratio to receive tezepelumab 210 mg or matching placebo.

Participants will be stratified by region (China, Japan, and Rest of World [ROW]), prior nasal polyp surgery and co-morbid asthma/AERD/NSAID-ERD. Randomisation will be monitored to ensure that 50%-70% of the study population will have co-morbid asthma/AERD/NSAID-ERD, and at least 50% will have had prior surgery for CRSwNP. When the target percentage of participants in a stratum in a region is reached, consideration will be given to closing the IWRS randomisation for that subgroup, which may be done either overall or within a specific region. Once a subgroup is closed, participants in the screening/run-in period in the closed subgroup will not be allowed to be randomised and will be screen failed.

[figure not shown]
After enrolment, eligible participants will enter a screening/run in period and will have their current inhaled corticosteroid (INCS) therapy standardized to mometasone furoate nasal spray (MFNS) or equivalent INCS at Visit 1 and throughout the screening and study period.

Participants who continue to meet eligibility criteria will be randomised at Visit 3 (Day 0) to receive either placebo or tezepelumab 210 mg SC at randomisation (Week 0) and every 4 weeks thereafter (Weeks 4, 8, 12, 16, 20, 24, 28, 32, 36, 40, 44, 48). A total of 13 doses will be administered. An end of treatment (EOT) Visit will be conducted at Week 52.

The first approximate 200 randomised participants will have a 24-week follow up (FU) period without investigational product (IP) administration to assess durability of benefit. These participants will have the final safety assessment at Week 76. The remaining participants will be followed for 12 weeks after the end of treatment visit, with the final safety assessments at Week 64.

An overview of the study design is provided below in [Figure 1](#).

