#### **2.1.3 Other Analysis Sets**

##### PK Analysis Set (PKS)

This analysis set comprises all participants in the FAS who received active (tezepelumab) treatment and had at least one detectable tezepelumab serum concentration from a sample

collected post-treatment that is assumed not to be affected by factors such as protocol deviations (PDs) (e.g. disallowed medication or incorrect study medication received). Summaries of PK will be based on the PK analysis set.

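### The Week 64 serum-concentration row mixes different washout times, because it sets no condition on time since last dose; this is a minor descriptive point

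*SAP*

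**What the plan says.** SAP 4.2.11.1 summarises tezepelumab concentrations by week over the on-study period, for the tezepelumab group. For the rows on treatment it admits "Only pre-dose samples at Weeks 4, 12, 24, and 36 and samples at Week 52 that were also between" 21 and 35 days after the previous dose. For the follow-up row the rule is "All samples for Week 64 that were taken within the visit window". PK is not among the variables given the sparse windows in SAP Table 2, so SAP Table 1 applies: Days 428-469, target Day 449.

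The same section handles non-quantifiable (NQ) values. If 50% or fewer at a time point are NQ, the geometric mean, CV, arithmetic mean and SD are calculated by "substituting the lower limit of quantification (LLOQ) divided by 2 for values which are NQ". "The LLOQ of tezepelumab in serum will be 0.010" µg/mL, so the substituted value is 0.005 µg/mL. The median, minimum and maximum are also reported.

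The PK analysis set (SAP 2.1.3) takes participants in the full analysis set who received tezepelumab and "had at least one detectable tezepelumab serum concentration from a sample" taken post-treatment and assumed unaffected by factors such as protocol deviations. It does not require completion of dosing. Protocol 7.1 says of early stoppers: "If study intervention is permanently discontinued, the participant will remain in the study to be evaluated for safety as per follow-up". Protocol 7.1.1 encourages them to attend all scheduled visits.

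**The concern.** At Week 52 the 21-35 day rule removes anyone who did not receive the Week 48 dose: a last dose at Week 44 is 56 days earlier. Nothing comparable applies at Week 64. The 21-35 day interval could not itself be used for a follow-up sample, so a different rule is reasonable; the gap is that there is no last-dose condition or split at all.

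A reader will naturally take the row as residual drug 16 weeks after the last dose. If early stoppers give Week 64 samples, the row pools participants at about 5 half-lives with others far beyond that. The geometric mean is sensitive to a few very low values, and the LLOQ/2 rule keeps cleared participants in it. Serum concentration is a stated secondary endpoint (SAP 1.1.3), so the row should describe one thing.

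**Working it through.** The documents give no expected concentration, CV or treatment-discontinuation rate, so there is no planned figure to reproduce.

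**From the documents**
- Half-life: Protocol 8.3.12.2 gives "until 16 weeks (5 half-lives) after the last administration of IP", so 112 / 5 = 22.4 days.
- Last planned dose: SAP 1.2 has dosing "every 4 weeks thereafter (Weeks 4, 8, 12, 16, 20, 24, 28, 32, 36, 40, 44, 48"; Week 48 is Day 337.
- Week 64 window: Days 428-469, target Day 449.
- LLOQ 0.010 µg/mL; NQ values entered as 0.005.

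**Assumed**
- Week 52 trough 20 µg/mL (range 10-40).
- Early stoppers supply 5% or 10% of Week 64 samples.
- Last doses spread evenly over Weeks 0-40 (early mix) or Weeks 24-44 (late mix).
- First-order elimination.

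**Step 1: time since last dose.** For a Day 337 dose: 449 − 337 = 112 days, or 5.0 half-lives; the window gives 428 − 337 = 91 to 469 − 337 = 132 days. Week 52 to Week 64 is 84 days, or 3.75 half-lives, so a completer is at 20 × 2^(−3.75) = 1.49 µg/mL. For a last dose at week w, the fold difference from a completer is 2^(7(48 − w)/22.4).

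| Last dose | Days to Day 449 | Half-lives | Fold below completer | µg/mL |
|---|---|---|---|---|
| Week 48 | 112 | 5.0 | 1 | 1.49 |
| Week 44 | 140 | 6.25 | 2.4 | 0.62 |
| Week 40 | 168 | 7.5 | 5.7 | 0.26 |
| Week 36 | 196 | 8.75 | 13.5 | 0.11 |
| Week 24 | 280 | 12.5 | 181 | 0.008, NQ, entered as 0.005 |

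**Step 2: geometric mean.** With share p and mean log ratio m of stoppers to completers, the geometric mean is multiplied by exp(pm).
- Late mix: log ratios −0.866, −1.733, −2.599, −3.466, −4.332 (Weeks 44 to 28) and ln(0.005/1.49) = −5.695 (Week 24); m = −3.115. At 5%: 1 − exp(−0.156) = 14%. At 10%: 1 − exp(−0.312) = 27%.
- Early mix: seven values at −5.695 (Weeks 0-24), then −4.332, −3.466, −2.599, −1.733; m = −4.727. At 5%: 21%. At 10%: 38%.
- Over troughs of 10-40 µg/mL, both mixes and between-participant CVs of 40-80%, the reduction is about 14-22% at 5% and 26-40% at 10%.

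**Step 3: CV.** The SAP does not say which CV it means. Start from an assumed 40%.
- Geometric: log-variance = s² + pv + p(1 − p)m², with s² = ln(1.16) = 0.148 and v the variance of the log ratios among stoppers (2.58 late, 1.98 early). At 5% the log-variance is 0.738 (late) or 1.309 (early), a geometric CV of about 105% or 164%. At 10% it is 1.280 or 2.358, about 161% or 309%.
- Arithmetic: with stoppers near zero, CV² becomes (CV² + p)/(1 − p). At 5%: √(0.21/0.95) = 47%. At 10%: √(0.26/0.90) = 54%.

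**Step 4: median.** Simulated with shares of 5-15%, troughs of 10-40 µg/mL and CVs of 40-80%, the median falls by only 2-14%.

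**The case against.** The strongest reply is that nothing inferential rests on this row. It is descriptive, its median is robust, and a minimum at the NQ level would be visible. SAP 4.2.5 lists dosing dates and SAP 4.2.11.2 lists concentrations over time with ADA status, so time since last dose can be worked out. All of this stands, and it is why the point is minor.

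Attendance is also uncertain. The three follow-up options after stopping treatment (Protocol 7.1.1) are described only up to Week 52. Protocol 7.1 keeps early stoppers in follow-up, so Week 64 samples are possible, but their number is unknown.

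Three stronger readings are tempting, and the documents do not support them:
- *The row would mislead interpretation of NPS and NCS off treatment.* Nothing in the documents links the two. The off-treatment analysis (SAP 4.2.9.1) uses the Additional FU Analysis Set, which requires the Week 64 visit but not completion of dosing, so early stoppers can be in it too.
- *Exposure-response is affected.* SAP 4.2.11.3 uses Weeks 24, 36 and 52 only.
- *Early stoppers are generally non-quantifiable.* At a 20 µg/mL trough this holds only for last doses at about Week 24 or before; a Week 40 stopper would be at about 26 times the LLOQ.

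**Conclusion.** The point holds as a minor improvement to a descriptive table. The Week 64 rule drops the control on time since dose that the Week 4 to Week 52 rows have, and no other section restores it. Given first-order elimination, any non-zero share of early stoppers is expected to lower the geometric mean and raise the CV, whichever CV is meant.

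Only the direction can be claimed from the documents. The 14-22% and 26-40% reductions rest on the assumed trough, share and stopping times, and on stoppers attending Week 64. A large inflation of the CV should not be asserted without first establishing that the SAP means a geometric CV. No efficacy, exposure-response or confirmatory result changes.

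**What to change.** In SAP 4.2.11.1, present the main Week 64 row for samples taken 91-132 days after the last dose, and show the remaining Week 64 samples in a separate row or listing with time since last dose. The interval is what a Week 48 dose on Day 337 gives across the full Day 428-469 window. A tighter 100-124 days (112 days, plus or minus the protocol's 5-day dosing and 7-day follow-up windows) would drop participants dosed at Week 48 whose samples fall elsewhere in the SAP's own window. It would help to state at the same time whether CV is geometric or arithmetic.

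The cost is a line or two of SAP text, one programming filter on dates that are already recorded, slightly fewer samples in the main row, and one extra row or listing.

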#### **4.2.11.2 Analysis of Immunogenicity**

All analyses of immunogenicity variables will be based on the safety set as defined in [Section 2.1.2](#). Results for China will be separated from results for all other countries (non-China).

The number of ADA positive participants at each visit will be summarised by treatment group for the on-study period. Descriptive statistics including number of participants, median, lower and upper quartile and range of the actual ADA titres by treatment group and visit, where possible, will be provided.

The ADA status across the study for each participant will also be classified and summarised by treatment group. Specifically, the following ADA results will be evaluated as number and proportion of participants in cohorts together with corresponding titre summaries:

- Participants who are ADA positive at any time including baseline (ADA prevalence)
- Participants who are ADA positive at baseline only
- Participants who are ADA positive at baseline and positive in at least one post baseline measurement
- Participants who are ADA positive at baseline regardless of post-baseline result
- Participants who are ADA positive post-baseline
- Participants who are ADA positive post-baseline and ADA negative at baseline (treatment induced ADA)

- Participants who are persistently positive; persistently positive is defined as having at least 2 post-baseline ADA positive measurements (with  $\geq 16$  weeks between first and last positive) or an ADA positive result at the last available post-baseline assessment
- Participants who are transiently positive; transiently positive is defined as having at least one post-baseline ADA positive measurement and not fulfilling the conditions for persistently positive
- Participants with treatment boosted ADA, defined as baseline positive ADA titre that was boosted to a 4-fold or higher level following IP administration
- Participants with treatment emergent ADA (ADA incidence): defined as either treatment induced ADA or treatment boosted ADA
- Participants who are nAb positive at baseline and/or post-baseline (nAb prevalence).
- Participants who are treatment-induced nAb positive (nAb incidence)

For ADA summaries at a single time point (eg, baseline ADA or by visit) the corresponding titre summary will be based on the titre of the positive sample for that particular visit. For summaries across visits (eg, ADA positive in an ADA category) the corresponding titre summaries will be based on the maximum titre of all positive samples for each participant.

Neutralizing ADA evaluations will be conducted on confirmed ADA positive samples. The test sample is deemed positive or negative for the presence of nAb to tezepelumab relative to a pre-determined (in assay validation) statistically derived cut point. The number and proportion of participants who are nAb positive at any time will be evaluated.

The ADA status across the study will be listed together with primary endpoints, biomarkers and serum concentrations over time, as well as with AEs/SAEs.

#### 4.2.11.3 Exposure-Response Analysis

Tezepelumab participants will be grouped according to drug concentration quartiles. The treatment groups referred to in the following analyses will be the drug concentration quartiles and placebo. Each drug concentration quartile will be compared against the overall placebo group. The same methods described in the primary analyses for the co-primary endpoints in Section 4.2.6.1 will be used.

The four, mutually exclusive, drug concentration quartiles will be derived using the median trough steady state drug concentration data. The median trough steady state is calculated as the median of the observed drug concentration data at weeks 24, 36 and 52 for each individual participant.

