4.2 Scientific Rationale for Study Design

This is a global study designed to investigate the safety and efficacy of fixed dose tezepelumab (210 mg) administered SC starting at randomisation and then every 4 weeks (Q4W) for a total of 13 doses, on top of standardised INCS, in participants with severe bilateral NP who remain symptomatic despite standard of care therapy. To avoid bias the study will be randomised and double blinded. The population is composed of participants with ongoing chronic symptoms for at least 8 weeks prior to enrolment with moderate to severe participant reported nasal congestion, and a physician endoscopic diagnosis of bilateral NP (NPS of at least 5 out of a maximum of 8), despite documented treatment with SCS within the past 2 years and/or history of any NP surgical intervention. The disease severity at enrolment and history of failure with standard pharmacological treatment constitute an accepted indication for surgery or for a targeted biologic therapy such as tezepelumab, for participants who are not willing to or are contraindicated to have surgery.

CRSwNP is a heterogeneous disease ([Hull and Chandra 2017](#)). The eosinophilic (Type 2 high) endotype is most common in the United States, Europe, and Japan whilst non-eosinophilic endotype is more frequent in other Asian countries ([Lou H et al 2018](#), [Hull and Chandra 2017](#), [Fokkens et al 2020](#), [Shin SH et al 2014](#), [Chitsuthipakorn W et al 2018](#)). To ensure that endotypes are represented appropriately in all countries in this study capping will be used in China to ensure that approximately 80% of participants have an eosinophilic endotype

(defined by JESREC score of ≥ 11) ([Tokunaga T et al 2015](#)) to match the distribution predicted in the rest of the world.

The sample size (approximately 400 participants) is considered appropriate to demonstrate treatment effects with tezepelumab. The 52-week treatment duration is considered appropriate to capture maintenance effects in this chronic disease, assessment of endpoints of time to first SCS use and/or surgery (and the individual components), and proportion of participants with resolution/near complete resolution of nasal polyps as well as providing 1-year treatment safety data in the intended population. Approximately the first 200 randomised participants will have a 24-week follow-up period to evaluate durability of response and to provide off-treatment safety data.

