### 1.3 Number of Participants

Approximately 400 participants will be randomised to tezepelumab 210 mg Q4W or matching placebo in a 1:1 ratio.

The study is sized to provide compelling statistical evidence for the co-primary endpoints (NPS and NCS) and key secondary endpoints of change from baseline in loss of smell, LMK, and SNOT-22 (considering a significance level of 0.01 in the sample size calculations), as well as sufficient power to assess the composite endpoint of time to SCS and/or surgery (2-sided level of 1%). In addition, this sample size allows assessment of the effect of tezepelumab vs placebo on NPS and NCS in key subgroups and provides a reasonably-sized safety database (CSP Section 9.2).

Assuming a population standard deviation (SD) of 2.25 in total NPS change from baseline and 1.22 in NCS change from baseline, this sample size of 200 participants per arm will provide at least 95% total power to observe a statistically significant difference at a 2-sided 1% level on both co-primary endpoints if the true effect of tezepelumab is -1.8 in total NPS change from baseline and -0.87 in NCS change from baseline. The assumption of true effects is based on reported estimates in the dupilumab Phase III nasal polyp studies. It is expected that treatment with tezepelumab will demonstrate similar or better treatment effects over a 52-week period. The assumed SD was estimated based on the CIs of the corresponding endpoints in the dupilumab Phase III nasal polyp studies ([Bachert et al 2019](#)).

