#### **3.1.6 Subgroups**

The following subgroups are defined for the purposes of efficacy subgroup analysis.

- Age category at screening visit (<65,  $\geq$ 65 years)
- Gender at screening visit (male, female)
- Race at screening visit (white, non-white)
- Prior surgery for NP status (yes, no)
- Allergic rhinitis at screening visit (yes, no)
- Co-morbid asthma/AERD/NSAID-ERD status at screening visit (yes, no)
- AERD/NSAID-ERD at screening visit (yes, no)
- Baseline eosinophil count (<150,  $\geq$ 150 to <300,  $\geq$ 300 eosinophils/ $\mu$ L)
- Baseline BMI (< 30 kg/m^2,  $\geq$  30 kg/m^2)
- Region (China, Japan, ROW)
- Region (Asia Pacific including China and Japan, Europe, North America)
- Baseline NPS (<median,  $\geq$  median)
- Baseline NCS (< median,  $\geq$  median)
- Time since last NP surgery at screening visit (<3 years,  $\geq$ 3 years)
- Number of previous NP surgeries (0, 1, 2 or more)
- Prior SCS use for NP (yes, no)

- Baseline weight quartiles
- Baseline staphylococcus aureus colonization in nasal culture (yes, no, not applicable)
- Baseline eosinophil count quartiles
- Baseline total serum IgE quartiles
- Baseline perennial specific IgE status:
  - Any perennial FEIA positive: requires 1 or more specific IgE (FEIA) panels to be positive. Provided that at least one IgE panel is positive, no further requirement is made for data on all 7 panels for all countries, excluding China, and all 6 panels for China only to be available.
  - All perennial FEIA negative: requires all 7 specific IgE panels to be negative for all countries, excluding China, and all 6 specific IgE panels to be negative for China.
  - If there are fewer than 7 panels for all countries, excluding China and less than 6 panels for China with data available and none of these is positive, then IgE status is considered “Unknown perennial FEIA”.
  - Positive is defined as a value  $\geq 0.35$  kU/L.
  - The 7 panels for all countries, excluding China include: IgE American Cockroach, IgE Cat Dander, IgE D. farina, IgE D. pteronyssinus, IgE Dog Dander, IgE German Cockroach, and IgE Mould Mix 1..
  - The 6 panels for China only include: IgE Dog Dander, IgE Cat Dander, IgE D. farinae, D. pteronyssinus, IgE German Cockroach, and IgE Mould Mix 1.
- Baseline seasonal specific IgE status:

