**Step 4:** In the datasets from Step 3, replace post-surgery score with WPS, and replace post-SCS/biologic for NP score with WOCF. If a participant received both NP surgery and SCS for NP/biologic for NP, scores post-surgery will be set to WPS.

Each of the imputed datasets at Week 52 will be analysed using the analysis of covariance (ANCOVA) model with treatment group, baseline co-morbid asthma/AERD/NSAID-ERD status, prior surgery status, and region as factors (based on eCRF), and the baseline value as a covariate. Rubin’s rule will be applied to combine analysis results (point estimates and standard errors) from the imputed datasets using PROC MIANALYZE.

Descriptive statistics including number of participants, mean, standard error, and least squares (LS) means will be provided at Week 52. In addition, difference in LS means (using the observed marginal distribution of the sample covariates) and the corresponding 95% confidence intervals (CIs) will be provided along with the p-value. A single asterisk (\*) will be used to denote a result that is statistically significant at alpha = 0.05 and a double asterisk (\*\*) will be used to denote a result that is statistically significant at alpha = 0.01. Nominal p-values will be presented unless specified otherwise.

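### The exposure-response analysis compares concentration quartiles only with placebo, so it cannot by itself show whether response depends on concentration

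*SAP*

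**What the plan says.** SAP 4.2.11.3 forms four tezepelumab groups by drug concentration. "The median trough steady state is calculated as the median of the observed drug concentration data at weeks 24, 36 and 52" for each participant. The contrasts are fixed in one sentence: "Each drug concentration quartile will be compared against the overall placebo group". On the model it says: "The same methods described in the primary analyses for the co-primary endpoints in Section 4.2.6.1 will be used".

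The SAP 4.2.6.1 ANCOVA has "treatment group, baseline co-morbid asthma/AERD/NSAID-ERD status, prior surgery status, and region as factors (based on eCRF), and the baseline value as a covariate". Neither weight nor BMI is in it. For each comparison it yields a difference in LS means, and "the corresponding 95% confidence intervals (CIs) will be provided along with the p-value".

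The section specifies no trend test, no contrast between quartiles and no model with concentration as a continuous variable.

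Other relevant text:
- Protocol 4.2 describes "fixed dose tezepelumab (210 mg) administered SC starting at randomisation", so dosing is not scaled to weight. Protocol 5.1 sets a floor of 40 kg and no ceiling.
- SAP 3.1.6 lists "Baseline weight quartiles" among the efficacy subgroups.
- Protocol 8.1.4 ends IP permanently at NP surgery, and SAP 4.2.6.1 sets post-surgery scores to the worst possible value.
- SAP 4.2.11.1 limits the Week 24, 36 and 52 samples in the PK summary table to those taken 21 to 35 days after the previous dose. SAP 4.2.11.3 does not repeat that limit.

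**The concern.** An exposure-response analysis is normally read as asking whether response differs between concentrations of the drug. A quartile-versus-placebo contrast asks whether that quartile differs from placebo, which is the treatment effect again in a quarter of the active arm. If the drug works as planned, every quartile will probably beat placebo even when concentration is irrelevant.

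The contrasts are also no longer randomised comparisons. Membership of a quartile is decided by samples from Weeks 24 to 52, while the placebo group is unselected. Anything that affects both concentration and outcome can produce a gradient that has nothing to do with exposure.

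At stake is what the study report can say about exposure-response in CRSwNP. Protocol 4.3 places the 210 mg Q4W dose on the plateau on the basis of asthma data. The planned contrasts could neither support nor contradict that for this disease.

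**Working it through.** **Inputs.** SAP 1.3 gives "this sample size of 200 participants per arm", SDs of 2.25 (NPS) and 1.22 (NCS), and effects of -1.8 and -0.87. Standardised effects are 1.8/2.25 = 0.80 and 0.87/1.22 = 0.713. Full PK data give 50 per quartile; 40 is used as an assumed lower case.

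**The plan's own figure.** The SAP claims at least 95% total power at two-sided 1%. The expected z is d × √(n/2): 0.80 × 10 = 8.0 for NPS and 0.713 × 10 = 7.13 for NCS, against a critical value of 2.576. Power exceeds 99.99% for each, which agrees with the claim.

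**One quartile against placebo, two-sided 5%.** Expected z = d × √(nq × 200/(nq + 200)).
- nq = 50: the root is 6.32, so z = 5.06 (NPS) and 4.51 (NCS). Power is 99.9% and 99.5%.
- nq = 40: the root is 5.77, so z = 4.62 and 4.12. Power is 99.6% and 98.5%.

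**Smallest significant observed difference, nq = 50.** 1.96 × SD × √(1/50 + 1/200) = 0.70 for NPS (39% of the planned effect) and 0.38 for NCS (43%).

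**All four contrasts together.** Quartile means and the shared placebo mean were simulated 200,000 times with 50 per quartile. Multipliers run from lowest to highest quartile and average 1. The trend test is the contrast (-3, -1, 1, 3) within the tezepelumab arm.

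| Quartile effect ÷ average | All four p<0.05: NPS | NCS | Within-arm trend p<0.05: NPS | NCS |
|---|---|---|---|---|
| flat | 99.6% | 97.9% | 5% | 5% |
| 0.8 to 1.2 | 97.9% | 93.7% | 40% | 33% |
| 0.6 to 1.4 | 85% | 76% | 92% | 85% |
| 0.4 to 1.6 | 52% | 43% | 99.9% | 99.5% |
| 0.2 to 1.8 | 17% | 14% | >99.9% | >99.9% |
| 0, then 4/3 in the other three | 2.5% | 2.5% | 99.9% | 99.5% |

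With 40 per quartile, the flat case gives 98.5% and 94.1%, and the 0.6 to 1.4 case gives 78% and 66%.

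**Possible size of weight confounding.** The documents give no correlation, so this is a range under assumptions. The mean of the top quarter of a standard normal is 1.271. A spurious highest-minus-lowest gap is 2 × 1.271 × r(weight, concentration) × r(weight, outcome) × SD, in absolute value.
- Assumed 0.3 and 0.1: 2 × 1.271 × 0.03 × 2.25 = 0.17 NPS points (0.09 for NCS).
- Assumed 0.7 and 0.3: 2 × 1.271 × 0.21 × 2.25 = 1.20 NPS points (0.65 for NCS).
- If weight is unrelated to outcome, the gap is zero.

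**Discontinuation.** A participant who stops IP at surgery but keeps attending (follow-up option 1, Protocol 7.1.1) can still be sampled at Weeks 24, 36 or 52, with falling concentrations. As SAP 4.2.11.3 is written, those samples enter the median. The same participant carries a score of 8 (NPS) or 3 (NCS). Low exposure and worst outcome then coincide because of the rules, whatever the drug does.

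**Power of a within-arm slope.** For a partial correlation of 0.2, z = atanh(0.2) × √(n - 3). With n = 200 this is 0.203 × 14.04 = 2.85, power 81%. With n = 160 it is 0.203 × 12.53 = 2.54, power 72%.

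**The case against.** Three arguments on the other side carry weight.

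First, a reader might infer that all four contrasts come out significant whether or not concentration matters. The arithmetic does not support that. With a steep gradient the lowest quartile often misses significance: all four succeed in only about half of trials or fewer at 0.4 to 1.6, and in about 2.5% if the lowest quartile has no effect. The contrasts fail to separate flat from mild-to-moderate, not flat from steep.

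Second, the output is more than p-values. The SAP 4.2.6.1 method reports LS mean differences and 95% CIs, and the four differences share one placebo group, so subtracting two of them gives a between-quartile estimate. A gradient can be seen by eye. What is missing is an estimate of that gradient with its own interval, adjusted for likely confounders.

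Third, a reader might infer that quartile differences are in fact confounded by body weight. The documents give neither a weight-concentration nor a weight-outcome figure, and the baseline score already in the model could absorb part of any association. The weight-quartile and BMI subgroup analyses (SAP 3.1.6, 4.2.6.6) will show whether the treatment effect varies with weight, though they do not adjust the concentration quartiles.

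It can also be said that SAP 4.2.11.3 states no hypothesis, and that calling the metric a steady-state trough implies on-dose samples. The first is true, and the question assumed here is the usual reading of the section's title. The second is not secured, because the rule given uses observed concentrations at three weeks without a dosing condition.

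**Conclusion.** The point holds in a limited form. At the planned effects and 50 per quartile, four significant quartile-versus-placebo results are nearly certain if response is flat (about 98-99.6%) and likely under a mild-to-moderate gradient (about 76-98%). They cannot by themselves show whether response depends on concentration. These figures rest on the SAP's effects and SDs, equal quartiles and a normal approximation.

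Differences between quartiles are open to confounding because the groups are formed after randomisation. Weight is a plausible source under fixed dosing but remains a risk, not an established bias. The route through surgery, low concentration and worst possible score follows from the plan's own rules, but its size cannot be computed from the documents.

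The analysis lies outside the testing hierarchy of SAP 4.1.2, so no primary or key secondary claim is affected. This is a worthwhile improvement, not a serious defect.

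**What to change.** In SAP 4.2.11.3:

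1. Add a within-tezepelumab estimate: the slope of change in NPS and in NCS on log median trough concentration, with 95% CI, adjusted for baseline score, baseline weight and the stratification factors. Report it mainly as an estimate. Power for a partial correlation of 0.2 is about 72-81% with 160-200 participants, and the trend results above show that a mild gradient would often go undetected.
2. Add baseline weight as a covariate in the quartile-versus-placebo ANCOVA, and label those contrasts descriptive.
3. Apply the 21-35-day post-dose limit of SAP 4.2.11.1 to the concentrations that define the median trough, so that off-dose samples do not define exposure. Weight adjustment cannot do this, and without it the slope in item 1 would inherit the surgery artefact.

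The cost is SAP wording, one covariate and one extra exploratory output, all on data already collected. Item 3 will leave some tezepelumab participants without a qualifying sample, so their number and reasons should be reported. The slope remains an observational comparison within the arm and should be described as such.
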